APPENDIX 6. DATA COLLECTION AND COLLECTION SCHEDULE

Data collected	FOLLOW-UP OF MATERIAL & PREGNANCY OUTCOME Enrollment until end of pregnancy					FOLLOW-UP OF OFFSPRING OUTCOMES Up to 12 months past-birth		
	Retrospective Follow-up *	Prospective follow-up				Prospective follow-up		
		Recruitment visit/contact	1 st trimester week 12 (± 2 wks)	2 nd trimester week 27 (± 2 wks)	3 rd trimester week 40 (± 2 wks)	0-3 months (± 1 month)	Month 6 (± 1 month)	Month 12 (± 1 month)
1. Informed consent	X	X						
2. Assessment of inclusion/exclusion criteria	X	X						
3. Collection of baseline characteristics	X	X						
4. Allocation of unique participant ID number	X	X						
5. Schedule interview with mother	X	X	X	X	X	X	X	X
6. Collection of maternal AEs	X		X	X	X			
7. Collection of pregnancy outcomes	X		X	X	X			
8. Review of prenatal booklet	X		X	X	X			
9. Collection of birth outcomes	X					X	X	X
10. Collection of neonatal & infant outcomes	X					X	X	X

* Data collection will occur only once since data is retrospective; however, it may be necessary to contact the mother/legal guardian post-interview for clarification purposes

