databases (secondary data sources). Study participation will require receipt of a signed informed consent form (ICF) or Assent form (AF) according to local regulations. CYD-TDV exposed pregnant women will be actively identified and recruited using pregnancy exposures reported to the national spontaneous adverse events following immunization reporting system (SI-PNI EAPV). As such, women included in the pregnancy registry will represent those receiving care in the public and private health care settings at the time of their pregnancy exposure. The start of follow-up for the pregnant women will be the date of first CYD-TDV vaccination during the exposed pregnancy and the date of birth for the offsprings. Study outcomes will include maternal, pregnancy, birth, neonatal and infant AESIs, as well as all other reported AEs. Study data will be collected by the study investigators (or research personnel designated by the investigators) through home visit and/or telephone interviews using a structured questionnaire. Self-reported information will be supplemented and confirmed through contact with the woman's physician or other health care provider (e.g., nurse), use of medical records (e.g., prenatal care booklet, hospital, primary health care unit or other settings where antenatal care was provided), and use of record linkages with existing databases (e.g., SINASC, SIM), subject to availability. In cases of discrepancies between data sources, the medical record will be used as the gold standard for most data, followed by databases. Women will be followed for 42 days after the end of pregnancy, irrespective of the duration of the pregnancy, and their offsprings will be followed for up to 12 months post-birth.

* Exact date will depend on timing of local and national EC approvals

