Participants' date of CYD-TDV immunization will be confirmed through probabilistic linkage (i.e., using nominal data) with the immunization registry; database linkages will be carried out by the DoH or study investigators depending on the availability of qualified personnel. When indicated, a women's self-reported exposure status will be reclassified using the immunization registry as the gold standard. In addition, reports of multiple CYD-TDV exposures during a pregnancy will be classified according to the earliest pregnancy exposure.

Women enrolled in the CYD-TDV pregnancy registry will be followed from the date of their first CYD-TDV vaccination during pregnancy (cohort entry) to up to 42 days following the end of the exposed pregnancy, regardless of the outcome of the pregnancy. The offspring of the exposed pregnancy will be followed for up to 12 months post-birth. In addition, women and offsprings enrolled prospectively (i.e., CYD-TDV exposure either soon before or after study start) will be followed until the earliest of: date of lost to follow-up, withdrawal of consent or death or end of study (July 2022).

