- **Pregnancy related events:** will be defined as study AESIs (see Appendix 2) and other reported adverse events (serious and non-serious) occurring during the pregnancy, labour and delivery, or the puerperium. Pregnancy related AEs will be classified as: (i) pregnancy outcomes, (ii) complications of pregnancy, and (iii) complications of labour, delivery and puerperium. These outcomes were chosen based on their frequent presentation, their importance as markers of maternal and/or infant health, and their public health relevance. In addition, chorioamnionitis and hypertensive disorders of pregnancy are major risk factors for preterm birth. The definitions used for these outcomes will be consistent with local clinical practice, the European Medicine Agency (EMA) and United States Federal Drug Agency (US FDA) pregnancy guidance documents, and other published pregnancy outcome classification systems such as the European Surveillance of Congenital Anomalies (EUROCAT).
- **Birth outcomes:** will be defined as study AESIs and other reported adverse events (serious and non-serious) observed or diagnosed at birth. See Appendix 3 for the list of birth outcomes of special interest and their definition.
- **Neonatal and infant events:** Neonatal events will be defined as study AESIs and other reported adverse events (serious and non-serious) occurring between the day of birth (DOB) and 28 days post-DOB. Study AESIs and other reported adverse events (serious and non-serious) occurring between day 29 and 365 post-birth will be classified as infant events. See Appendix 4 for the list of neonatal and infant events of special interest and their definition.

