control access to the study database to ensure data integrity. After integration of all corrections in the primary data dataset, and after AE information available from CDM and the GPV Department has been reconciled, the primary data database will be released for statistical analysis. Review of the data from primary data sources is anticipated to take place through the data review process led by Data Management.

For women and offsprings enrolled retrospectively (i.e., outcomes occurred prior to study enrollment), their primary data will be obtained all at once (i.e., one interview) owing to the retrospective nature of the data; however, it may be necessary to contact the mother/legal guardian post-interview for clarification purposes. For women and offsprings enrolled prospectively (i.e., outcomes occurring after enrollment), the data will be collected at pre-specified time points during pregnancy (at enrollment, 1st, 2nd and 3rd trimester). For outcomes in the offsprings, data will be collected within 3 months (± 1 month) of birth, then at 6 months (± 1 month) and 12th months (± 1 month) post-delivery.

Details of the data to be collected and the data collection schedule can be found in Appendix 6.

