9.6.2 Participant tracking log

The list of CYD-TDV exposed pregnant women obtained from Paraná's DoH will also serve as the electronic participant tracking log. The following information will be documented in the tracking log: (i) participant unique, anonymized study ID number; (ii) availability of valid contact information (yes/no); (iii) eligibility status (yes/no); (iv) outcome of each contact attempt and contact dates; (v) participation status (yes/no); (vi) reason(s) for non-participation (e.g., unsuccessful contacts, refused, no signed ICF/AF); (vii) follow-up type (prospective/retrospective/both) if applicable; (viii) withdrawal status (yes/no) if applicable; (ix) study withdrawal date (if applicable); (x) reason(s) for withdrawal (if applicable); (xi) loss to follow-up status (yes/no), and (xii) date of loss to follow-up (if applicable). This information will be used to prepare the study cohort flow diagram.

To comply with data privacy requirements, data collected on the tracking log will be fully anonymized. As such, the final tracking log will not include any nominal data and study participants will be identified using only their unique, anonymized study identification number.

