Maternal death	
 • Maternal death during pregnancy or ≤ 42 days of delivery; derived from maternal date of death and infant DOB

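### For prospectively followed women, no maternal or pregnancy-outcome collection is scheduled after the week-40 contact, although follow-up and puerperal endpoints run to 42 days after the end of pregnancy

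*Protocol*

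**What the plan says.** **What is promised.** Protocol section 9.1.1: "Women will be followed for 42 days after the end of pregnancy, irrespective of the duration of the pregnancy". Section 9.2.2 repeats the window: "up to 42 days following the end of the exposed pregnancy, regardless of the outcome of the pregnancy". Section 9.3.1 defines pregnancy related events, part of the primary endpoint, as those "occurring during the pregnancy, labour and delivery, or the puerperium". Appendix 2 includes postpartum hemorrhage, chorioamnionitis and maternal death among the events of special interest. It defines the last as "Maternal death during pregnancy or ≤ 42 days of delivery", to be "derived from maternal date of death and infant DOB".

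**What is scheduled.** Section 9.6.1 says that for prospectively enrolled women "the data will be collected at pre-specified time points during pregnancy (at enrollment, 1st, 2nd and 3rd trimester"). It describes the later contacts (within 3 months of birth, then months 6 and 12, each ±1 month) for offspring outcomes only. The maternal block of Appendix 6 is headed "FOLLOW-UP OF MATERIAL & PREGNANCY OUTCOME Enrollment until end of pregnancy". Its rows for maternal adverse events, pregnancy outcomes and prenatal-booklet review are marked for prospective women at weeks 12, 27 and 40 (±2) and blank at 0-3, 6 and 12 months. The row for scheduling an interview with the mother is marked at those three later contacts, as are birth, neonatal and infant outcomes.

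**Retrospective women** have one interview. The tracking log in section 9.6.2 allows "follow-up type (prospective/retrospective/both) if applicable", but neither section 9.6.1 nor Appendix 6 says how the mixed type is scheduled.

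**The concern.** The table and section 9.6.1 agree with each other and disagree with sections 9.1.1, 9.2.2 and 9.3.1 and Appendix 2, so this is not a stray blank cell. Staff who work from the schedule would interview the mother after birth without being directed to ask about her own labour, delivery or puerperium.

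At stake is the rate of labour, delivery and puerperal events in the prospective stratum. Sections 9.7.1 and 9.7.4 set that stratum against the retrospective one to gauge bias. If a pregnancy has a known outcome but its puerperium was never asked about, it can stay in the denominator while its late events are missed. A lower prospective rate could then reflect the schedule and not recall or detection bias among retrospective women.

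**Working it through.** The protocol gives no figure for this point, so there is none to reproduce. The check is calendar arithmetic.

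**Inputs.** Promised window: 42 days = 6 weeks after the end of pregnancy (sections 9.1.1, 9.2.2). Last marked maternal contact: week c = 40 ± 2, so 38 to 42 (Appendix 6). Pregnancy ends at gestational week g.

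**Formulas.** Promised follow-up ends at week g + 6. Postpartum days that the last contact can look back on = max(0, min(42, 7 × (c − g))). If g > c, the woman is still pregnant at that contact.

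| Pregnancy ends (g) | Follow-up should end | Days covered, c = 38 | c = 40 | c = 42 |
|---|---|---|---|---|
| 32 | week 38 | 42 | 42 | 42 |
| 34 | week 40 | 28 | 42 | 42 |
| 36 | week 42 | 14 | 28 | 42 |
| 37 | week 43 | 7 | 21 | 35 |
| 38 | week 44 | 0 | 14 | 28 |
| 39 | week 45 | still pregnant | 7 | 21 |
| 40 | week 46 | still pregnant | 0 | 14 |
| 41 | week 47 | still pregnant | still pregnant | 7 |
| 42 | week 48 | still pregnant | still pregnant | 0 |

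Full coverage needs g ≤ c − 6: week 32, 34 or 36 for a contact at week 38, 40 or 42. From week 37 on, even the latest permitted contact falls short.

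**Early endings.** Pregnancies ending by week 32 are covered only if the week-based contacts continue after the pregnancy is over. The Appendix 6 heading and the wording of section 9.6.1 leave that unclear.

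**Stillbirth after the last contact.** The remaining contacts are offspring contacts counted from birth, and SINASC is a live-birth registry (section 9.4). No scheduled contact picks this outcome up, although section 11.1.1 always treats it as serious.

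**Maternal death.** After a miscarriage or ectopic pregnancy there is no infant date of birth, so the derivation in Appendix 2 lacks an input. On section 9.5's own rate, spontaneous abortion alone is 1/7 = 14.3% of pregnancies (31 of 214 in its table).

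**How many women are affected.** The last campaign ended in June 2018 (section 7.2). In the latest case, exposure is on 30 June 2018, 30 days before the last menstrual period on 30 July 2018. Delivery at week 42 (294 days) is then 20 May 2019, and day 42 is 1 July 2019. Enrollment opens in July/August 2019 (section 6), so every campaign exposure to date has passed its maternal window by then. Prospective mothers would have to come from later campaigns or other later vaccination.

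**Infants.** Those born after July/August 2018 are under 12 months at the earliest interview date, which includes late births from the 2018 campaign. These mother-infant pairs need a stated rule.

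**The case against.** A reader might infer that puerperal events are simply not collected. The documents do not support that.

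- Section 11.1.3.1 requires all adverse events to be recorded from consent to the end of each participant's collection period.
- The mother is interviewed at 0-3 months and birth outcomes are taken then, so the ending of a live-birth pregnancy is learned even if it falls after the week-40 contact.
- Section 9.3.1 bases diagnoses on clinician assessment in records or databases. Appendix 2 ties chorioamnionitis to the delivery hospitalization and allows postpartum hemorrhage to be established from the record.
- SISPRENATAL holds puerperium visits and SIM holds deaths. No interview row would help to find a mother who has died.

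Much of this stands, and it limits the point to systematic interview-based ascertainment. It does not close the gap. The adverse event rule refers back to a collection period on which the sections conflict, and it sets no time for asking. SISPRENATAL covers the public sector only, and section 9.8.1 says visits after the first are less completely recorded than in the prenatal booklet. Section 9.7.4 says private-sector outcome data will be limited to self-report, which is what the schedule omits. The 0-3 month contact may also fall before day 42.

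Three further inferences go too far. The 14.3% is the share of pregnancies for which the stated derivation lacks its input, not a share of maternal deaths missed; SIM supplies dates of death. A definite bias toward zero is not established either: section 9.8.1 expects closer surveillance to raise detection, and section 9.7.1 restricts the pregnancy-outcome denominator to known outcomes. Lastly, the single retrospective interview need not bar later contact with a young infant, since Appendix 6 has prospective offspring columns. That point is an ambiguity.

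**Conclusion.** The inconsistency is real and should be fixed, but it does not undermine the study. For prospective women delivering at week 37 or later, between 7 and 42 of the 42 days have no scheduled maternal collection, depending on delivery week and contact timing: 7 days at best (delivery at week 37, contact at week 42), all 42 at worst. A stillbirth after the last contact has no scheduled contact. Puerperal event rates in that stratum may be under-ascertained, most plausibly among private-sector women. By how much cannot be computed from the protocol, because it depends on how complete the records and linkages are.

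The conclusion assumes that staff collect what the schedule marks and that contacts fall within the stated windows. The retrospective stratum, which section 9.9 expects to supply the majority of outcomes, is untouched by this gap. The prospective maternal stratum may be small or empty, since section 9.2.4 makes it conditional on further campaigns. This keeps the severity moderate.

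**What to change.** Reconcile section 9.6.1 and Appendix 6 with sections 9.1.1, 9.2.2 and 9.3.1:

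1. In Appendix 6, mark maternal adverse events, pregnancy outcomes and record/booklet review at the existing 0-3 month contact, and require that contact to fall on or after day 42. Extend the block heading to 42 days after the end of pregnancy and amend section 9.6.1 to match. All 42 days are then covered after a live birth, whatever the gestational age.
2. Add one contact at or after day 42 for pregnancies that end without a live birth, including stillbirth.
3. In Appendix 2, derive maternal death from the end-of-pregnancy date instead of the infant's date of birth.
4. State that infants under 12 months at a retrospective interview follow the prospective offspring contacts up to month 12, and that these pairs take the mixed follow-up type in the tracking log.

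The cost is a few questions at an interview already scheduled with the mother, one telephone call per pregnancy without a live birth, and a further contact for some young infants. No analysis method or sample size changes.
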